7.2 Vital Signs

Vital signs will include measurements of sitting blood pressure, sitting respiratory rate, temperature, and sitting pulse rate. Vital signs will be collected during treatment times and are explained in Section 7.7on Clinical Observations.

7.3 Kt/V

Weekly stdKt/V_{urea} will be calculated from pre- and post-dialysis urea levels. Blood samples will be obtained once a month mid-week. A central laboratory will be used for the analysis of the blood samples. If the weekly stdKt/V_{urea} goal (\geq 2.0) is not met, the reason will be recorded.

Clinic personnel or designee will be trained to obtain the pre- and post-treatment blood samples based on the Kidney Disease Outcome Quality Initiative Guidelines for sample collection.

7.4 Training on the HemoCareTM Hemodialysis System and Study Procedures

[figure not shown]
7.4.1 Study Site Team Training

HemoCare™ Hemodialysis System training tools developed specifically for use with the system will be utilized. All assigned new site team members will receive study training specific to their study role (e.g., protocol, eCRF, laboratory procedures) prior to starting study activities.

7.4.2 Subject and Care Partner Training

Enrolled subjects and care partners will receive refresher training (if Investigator deems necessary) on an as-needed basis by approved site training nurses. If a new care partner requires training, training will be provided by approved site training nurses.

7.7 Clinical Observations

Each time a subject is dialyzed with HemoCareTM Hemodialysis System, the following information will be obtained from HemoCareTM Connectivity Platform and Treatment Flowsheet:

- Medications given during or immediately after treatment
- Anticoagulation regimen
- Treatment interventions
- Patient weight: pre- and post-dialysis (if unable to enter post-dialysis weight in device, subject will note the weight on the Treatment Flowsheet)
- Blood pressure: both pre and post-dialysis seated
- Pulse: both pre-dialysis and post-dialysis seated
- Body temperature: pre- and post-dialysis

A study nurse or their designee will collect study data monthly (minimum) as detailed in the section below. The Investigator or designee will assess each subject on a weekly basis according to care plan (see Section 7.8). The assessment may include blood pressure, fluid status, and dialysis prescription.

7.8 Treatment Flowsheet and Weekly Assessment

At every treatment with the HemoCareTM Hemodialysis System, subjects will complete a Treatment Flowsheet to document certain data. In addition, the Investigator or designee will perform a weekly assessment of each enrolled subject. Sites may choose to communicate more frequently with the study subjects per local requirements or standard-of-care. At a minimum, the Investigator or qualified designee must communicate with the subject weekly to review and discuss the following:

- Subject status/condition updates potential AEs experienced
- Treatment interruptions
- Confirmation if the subject contacted the dialysis center for support with a device or health related issue
- Any changes to current medications, including those taken since the last Weekly Assessment
- Current treatment inventory needs, including any components with expiration dates coming up

This data will serve as supplemental source documentation for the sites to support consistent data collection during Evaluable Periods.

Sites may choose to communicate more frequently with the study subjects per local requirements or standard-of-care. At a minimum, the Investigator or qualified designee must communicate with the subject weekly. Based on all data collected from the subject, the site staff will complete their source logs and eCRFs as appropriate.

7.9 Water and Dialysate Sampling Analysis

Tap (feed) water used to feed the HemoCare™ Water Device shall meet EPA standards for drinking water. Product water shall not exceed the chemical contaminant levels as stated in the ANSI/AAMI 13959:2014 standard.

The Sponsor or its designee will train the person(s) responsible for collecting the water and

dialysate samples during the study. Instructions will be provided in the study training materials. Standardized recovery methods and positive and negative controls will be incorporated into the testing protocol(s). A central laboratory will be used for all water and dialysate testing.

Sample results will be sent to the study sites and Sponsor for real-time review and action (if appropriate). Observations and decisions regarding corrective measures (e.g., re-culture, consumables replacement, and/or disinfection of either device) will be based on the organism growing, whether or not bacterial or endotoxin levels exceed the specified guidelines, and any clinical symptoms the subject may have. A Safety Management Committee will also review study wide results per the Safety Management Plan to search for trends and to action appropriately.

[figure not shown]
Analysis of water and dialysate will be performed on samples obtained as follows.

7.9.1 Chemical Contaminants - Tap Water

Tap water samples will be collected and tested from all actively participating locations, at a minimum, yearly or as required by site policy or local regulations. Trial subjects can continue treating on HemoCareTM Hemodialysis Systems in these locations while the results are being analyzed.

7.9.2 Microbiological Cultures and Endotoxin – Ultrapure

will be collected from the device by Sponsor personnel or designees at least quarterly or according to local procedures after subject rolls over from DEKA Protocol DKPL-00057-001 study. If a new, not previously qualified, HemoCare™ Hemodialysis System is installed in the subject's home, the subject cannot be treated with the HemoCare™ Hemodialysis System until the results are received and reviewed by the trial site and Sponsor per the device User Guide. Once a HemoCare™ Hemodialysis System has been installed and passes the ultrapure microbial and endotoxin analysis, any replacement device (e.g. replacement treatment device or water device) will not require ultrapure samples to be recollected unless source water has changed.

System shall not exceed microbial or endotoxin levels as stated in ANSI/AAMI/ISO 23500-5:2019 standard. Based on this standard, the acceptable limit for microorganisms is < 0.1 CFU/mL and the acceptable limit for endotoxin is < 0.03 EU/mL.

7.9.3 Process for Responding to Out-of-Specification Results

7.9.3.1 Decision Tree

Clinical study decision trees for ultrapure	samples have been developed and will be
provided to study sites. These decision tr	rees provide guidance to the clinical site
and the DEKA R&D	team on appropriate actions to be taken
in situations where OOS results are receiv	red from ultrapure
Upon confirmation of an OOS value for e	•
in approach	

Additional actions are described as follows:

- Resample.
- All device logs evaluated for anomalies.
- Procedure checklists recorded during sample collection and processing reviewed for anomalies.
- Contract Laboratory will conduct an independent investigation of their procedures and processes for any OOS endotoxin or micro-organism result.
- Consideration for additional actions such as retrieval and analysis of hardware and/or disposables, on site investigation for additional machine and environmental cultures, etc.

7.9.4 Chloramine, pH, and Conductivity Testing

Chloramine testing of the water for dialysis will be completed according to standard-of- care and local requirements.

8 ADVERSE EVENT REPORTING

8.1 Adverse Events and Serious Adverse Events

An AE is any untoward medical occurrence in a subject administered a study product and which does not necessarily have a causal relationship with the treatment or study product.

An AE can therefore be any unfavorable and unintended sign (including an abnormal laboratory function), symptom (e.g., rash, pain, discomfort, fever, dizziness, etc.), disease (e.g., bacteremia, pancreatitis, etc.) or outcome of death temporally associated with the use of the study product, whether or not the event is considered to have a causal relationship with the study product.

Laboratory and vital sign abnormalities qualify as AEs if medical intervention is required to treat or address the abnormality, if the subject must be discontinued from the study due to the abnormality, or if the value exceeds specific limits defined by the protocol as qualifying it as an AE (see Appendix 4).

An elective procedure/surgery that occurs during the course of a study but is being performed for a documented pre-existing condition and was pre-planned prior to study entry will not qualify as an AE. If, however, the pre-existing condition unexpectedly deteriorates during the study requiring the procedure/surgery to be performed earlier than planned, the condition for which the procedure/surgery is being performed will qualify as an AE.

Adverse events will be collected starting from the time the subject signs the ICF until the end of the study. If an AE occurs, a full description of the event should be recorded including the date of onset, severity, time course, description, actions taken, and causal relationship of the AE to the study product(s). Investigators should review and reference the Causality definitions below when determining relationship of the AE to the study product. The Investigators may also discuss the event(s) with the Medical Monitor, but the Investigator must make, document and report the relationship for every AE. All AEs must be documented in source documents and on the eCRFs, no matter how common they are for a particular subject and regardless of the causality assigned by the Investigator.

All AEs and SAEs, regardless of relatedness, should be actively solicited and recorded.

Additionally, any AE voluntarily reported by the subject should be recorded and verified by the Investigator or designee on the appropriate source documents and eCRF pages.

The outcome/resolution of all AEs and SAEs will be determined by the Investigator and documented on the AE eCRF. Investigators will be instructed to follow all AEs/SAEs as follows: Unrelated AEs will be followed until resolution or until the end of the study whichever occurs first. Adverse device effects (related AEs) and all SAEs (related or not) will be followed until resolution or stable, including following the subject after the end of the study 30 days post study completion. The outcome categories that can be chosen on the eCRF by the Investigator include: Fatal, Not recovered/Not resolved (this outcome is reached for AEs which are ongoing when the subject's End of Study is due to death related to another AE), Recovering/Resolving (this outcome is reached for AEs which are ongoing at the subject's End of Study), Recovered/Resolved with Sequelae (if there are some residual effects caused by the event), Recovered/Resolved, and Unknown.

All SAEs regardless of their relationship to the study product will be submitted to the Sponsor by the Investigator or designee within 24 hours of becoming aware of the event. If an investigator becomes aware after study completion of an SAE that occurred in a subject during their participation in the study, the SAE must be reported on the SAE Form within 24 hours after awareness. Serious adverse events occurring within 30 days of study completion (per subject) must also be reported.

An AE can result from the use of the study product in accordance with the protocol, as well as from an accidental or intentional misuse of the study product or any other treatment error such as unintentional administration or use of another product during the course of the study.

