7 STUDY ACTIVITIES

7.1 Demographics and Baseline Characteristics

Medical history and medications will be reviewed and updated as necessary. Demographics (age, gender, race, and ethnicity) were recorded in DEKA Protocol DKPL-00057-001. For this study, baseline observation data for all assessments are defined in section 11.4 and unless otherwise specified therein, are the last observational values brought forward from DEKA Protocol DKPL-00057-001. Physical Examination

Physical examinations will be performed at End of Study visit.

An attempt should be made to perform a final physical examination on subjects who discontinue from the study early, particularly if the subject is discontinuing from the study because of an AE.

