8.1.10 Adverse Event Reporting

8.1.10.1 Reporting Adverse Events to Sponsor/Designee

During the course of the study, the Investigator or designee will routinely monitor each subject for the occurrence of any AE/ADE. If an AE/ADE occurs, the Investigator or designee will complete the AE eCRF which includes the following:

- · Description of the event
- Start and stop date of the event
- Timing of the event (prior to first study treatment, during treatment setup, during treatment, within 4 hours after treatment ends, > 4 hours after treatment ends)
- Seriousness of the event (yes, no)
- Severity of the event (mild, moderate, or severe)
- Causality of the event (related to treatment and/or related to the IP)
- Action taken
- Outcome of the event (fatal, not recovered/not resolved, recovered/resolved with sequelae, recovered/resolved, and unknown)

All SAEs must be reported to the Sponsor/designee within 24 hours of the Investigator or designee becoming aware of its occurrence. The informed site team member should also contact their site monitor by phone or email to notify him/her of the event. This requirement is irrespective of whether the AE is thought to be possibly related to the study product or not.

[figure not shown]
8.1.11 Expedited Reporting of Serious Adverse Events and Suspected Unexpected Serious Adverse Reaction (SUSAR)

The Sponsor/designee will assess each SAE reported by the Investigator to determine if the SAE qualifies as an expedited report according to FDA criteria. Sponsor/designee will report to FDA according to the applicable time requirements.

Per regulations, when an Unexpected Adverse Device Effect (UADE) or SUSAR occurs Investigators will receive a letter from Sponsor/designee describing the UADE/SUSAR. The Investigator should file this letter within their Investigator Study Binder. Additionally, the expedited report letter should be submitted by the

Investigator to their IRB/REB, as appropriate per FDA regulations.

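### Section 8.1 assigns AEs still ongoing when a living subject leaves the study to 'Recovering/Resolving' without requiring improvement, and Section 8.1.10.1 omits that category from the same AE eCRF

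*Combined protocol and SAP*

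**What the plan says.** Section 8.1 makes the outcome of every AE the investigator's decision and names the form: "The outcome/resolution of all AEs and SAEs will be determined by the Investigator and documented on the AE eCRF". It then lists six categories: fatal, not recovered/not resolved, recovering/resolving, recovered/resolved with sequelae, recovered/resolved, and unknown. Two of them concern AEs that are still ongoing, and each carries a rule in parentheses:

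- For *Not recovered/Not resolved* the rule given is: "this outcome is reached for AEs which are ongoing when the subject's End of Study is due to death related to another AE".
- For the other: "Recovering/Resolving (this outcome is reached for AEs which are ongoing at the subject's End of Study".

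On follow-up, Section 8.1 says "Unrelated AEs will be followed until resolution or until the end of the study whichever occurs first". Adverse device effects and all SAEs are followed longer, until resolved or stable, including 30 days after study completion.

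Section 8.1.10.1 describes what is entered when an AE occurs: "the Investigator or designee will complete the AE eCRF which includes the following". Its outcome item reads "Outcome of the event (fatal, not recovered/not resolved, recovered/resolved with sequelae, recovered/resolved, and unknown". That makes five categories, and *Recovering/Resolving* is not among them.

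**The concern.** The two categories for ongoing events are separated by why the subject's participation ended, not by the state of the event. An AE that is unchanged or getting worse when a subject leaves alive meets the only condition stated for *Recovering/Resolving*, and does not meet the one stated for *Not recovered/Not resolved*. The coded outcome would then read as improvement that nobody observed.

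The two sections also disagree about which categories the form offers. In a multi-center study, a site working from 8.1 and a site working from 8.1.10.1 could code the same event differently.

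The study's stated objective is safety under continued access to the device. The recorded outcome of an AE that had not resolved at exit is part of that evidence, and as drafted it would not show whether the event was improving.

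**Working it through.** The plan gives no figure to reproduce on this point. The check compares the two lists and then follows one event through each section.

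**Lists side by side**

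| Outcome category | Section 8.1 | Section 8.1.10.1 | Condition given in 8.1 |
|---|---|---|---|
| Fatal | yes | yes | none |
| Not recovered/Not resolved | yes | yes | ongoing at a death related to another AE |
| Recovering/Resolving | yes | **no** | ongoing at End of Study |
| Recovered/Resolved with sequelae | yes | yes | residual effects remain |
| Recovered/Resolved | yes | yes | none |
| Unknown | yes | yes | none |
| Total | 6 | 5 | 3 of 6 |

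The difference is 6 − 5 = 1 category, *Recovering/Resolving*. Nothing in the 8.1.10.1 list is absent from 8.1. Of the three categories with a condition, two concern ongoing AEs. Neither of those two mentions whether the event is improving.

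**Are both lists for the same form?** Yes. Both sections name the AE eCRF.

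**One event followed through.** Take an AE known to be ongoing and not improving in a subject who leaves the study alive.

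1. Under 8.1, the condition for *Recovering/Resolving* (ongoing at End of Study) is met.
2. The condition for *Not recovered/Not resolved* (End of Study due to death related to another AE) is not met.
3. *Unknown* does not describe it, because the status is known. The remaining three categories are fatal or recovered.
4. So the 8.1 guidance leads to *Recovering/Resolving*.
5. Under 8.1.10.1 that option is not listed. What remains is *not recovered/not resolved*, whose 8.1 condition is not met, or *unknown*, although the status is known.

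Restricting the rule to living subjects is an inference from the contrast between the two parentheses. The text for *Recovering/Resolving* does not itself exclude death.

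**Can the case arise?** Yes. Section 7.1 asks for an attempt at a final physical examination in subjects who leave early, "particularly if the subject is discontinuing from the study because of an AE". Appendix 1 carries AEs still ongoing from the parent study into this one, so persistent events are expected. Appendix 4 lists access aneurysm and defines it as a progressive condition.

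**Where is the label final?** For unrelated non-serious AEs, because 8.1 ends their follow-up at the end of the study. For adverse device effects and SAEs the outcome can still be updated, though their follow-up may stop at stable, which is not the same as improving.

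**Which planned summaries use outcome?** Section 11.5.1 uses SOC, PT, seriousness, severity, anticipated status and relatedness. It does not use outcome. Planned summaries affected: 0.

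**The case against.** The strongest reply is that the text is permissive. Section 8.1 speaks of categories the investigator can choose, introduces them as an inclusive list, and never says *only*. Section 8.1.10.1 likewise does not claim its list is complete. The eCRF and its completion instructions are not in the documents, so the form may already be right. This stands in part: an investigator could choose another category. But the parentheses are the only guidance given. They describe no category for a known, non-improving AE in a living subject, and an inclusive list does not explain why a category named in one section is missing from the other.

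A second reply is that other fields limit the damage. Section 8.1 requires "a full description of the event should be recorded including the date of onset, severity, time course, description, actions taken". The eCRF also takes start and stop dates, and the reason for discontinuation is recorded separately. An ongoing AE should have no stop date, so the label does not hide that it is unresolved. This also stands in part. A blank stop date shows that the event continues, not whether it is improving. The time-course description can show that, but a reader relying on the outcome field alone would be misled.

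A third reply is that the affected group is narrow, no planned analysis changes, and no listing or narrative by outcome is described in the documents. This is correct, and it is why the point is minor.

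**Conclusion.** The concern holds on both parts. The rule for *Recovering/Resolving* is wrong as written, because it gives a favourable label to any AE ongoing at exit. The two outcome lists for the same form also contradict each other by one category.

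The severity is minor. The effect is confined to the recorded AE outcome and any listing or narrative that draws on it, mainly for unrelated non-serious AEs ongoing at exit in subjects who leave alive. The documents give no number or proportion of AEs that would be ongoing and not improving at exit, so the size of the affected group cannot be stated.

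The conclusion rests on reading the two parentheses as the guidance sites will follow. If the eCRF or its instructions already define the categories by event status, the remaining task is to correct the protocol text to match.

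**What to change.** In Section 8.1, define the two ongoing categories by the status of the event at the investigator's last assessment:

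- *Recovering/Resolving*: ongoing and improving.
- *Not recovered/Not resolved*: ongoing and unchanged or worse, including when ongoing at a death from another cause.

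Use the same six categories in Section 8.1, Section 8.1.10.1 and the AE eCRF.

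The cost is a small wording change in two sections and a check that the form's list agrees. Some AE outcomes will read less favourably than under the present rule. No planned analysis has to be altered.

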8.1.1 Definitions of Adverse Event Terms

Study Product: For this protocol, the term "study product" is synonymous with IP.

Date of Onset: The date that the signs and symptoms of the AE began.

Severity: Severity will be assessed for each AE and defined using the following criteria:

Mild – Asymptomatic. A transient discomfort and does not interfere in a significant manner with the subject's normal functioning level. The AE resolves spontaneously or may require minimal therapeutic intervention.

Moderate – Produces limited impairment of daily function and can require minimal, local or non-invasive therapeutic intervention, but produces no sequelae.

Severe or Medically Significant – Requires hospitalization or prolonged hospitalization. Results in a marked impairment of function and can lead to temporary inability to resume usual life pattern. The AE produces sequelae requiring (prolonged) therapeutic intervention.

Causality:

Causality Assessment – A determination is made bythe Investigator and sponsor as to whether there is a reasonable possibility that the device or drug is etiologically related to/associated with the AE. Causality assessment includes, for example, assessment of temporal relationships, association (or lack of association) with underlying disease, treatment association (or lack of association), presence (or absence) of a more likely cause, and physiologic plausibility. Categories for causality assessment are "probably associated," "possibly associated," "unlikely associated" and "not associated."

Related: An AE follows a strong temporal relationship to the device or drug, and another etiology is unlikely or significantly less likely.

Possibly Related: An AE follows a reasonable temporal relationship to the device or drug, and an alternative etiology is equally or less likely compared to the potential relationship to the device or drug.

Unlikely Related: An AE has little or no temporal relationship to the device or drug and/or a more likely alternative etiology exists.

Not Related: An AE that is due to underlying or concurrent illness, complications, concurrent treatments or effect of another concurrent drug/therapy and is not associated to the device or drug (i.e., does not follow a reasonable temporal relationship to the use of the device or drug, or has a much more likely alternative etiology).

